10.2 Populations for Analyses

Subjects will be analyzed by gender, demographics, and by site to ensure that results are consistent across these variables.

10.3 Statistical Analyses

10.3.1 Performance Endpoint Analysis

Although not a randomized study, each subject dialysis session will be performed using either the test needle or a control needle. The sites are instructed to perform 3 control sessions first and then 6 test sessions per enrolled subject, and in the case that a site deviates from this order, performance measure will be analyzed based on the needle used. Assuming there will be a 20% rate of attrition/drop-out, the remaining 18 subjects would contribute 108 test and 54 control sessions. Data will be pooled by session type (test vs. control) from all sites (no by-site analyses are planned).

The primary performance analysis will test the non-inferiority hypothesis as a difference of proportions between the test and control groups using a one-sided Farrington-Manning Score Test at a significance level of $\alpha=0.025$.

Additionally, the primary performance measure will be analyzed on the subject-level (utilizing a non-inferiority margin of 0.05) by testing the difference in mean success rates per subject across treatment groups using a one-sided paired t-test at a significance level of $\alpha=0.025$.

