6.2 Exclusion Criteria

An individual who meets any of the following criteria will be excluded from participation in this study:

1. Subjects receiving chronic hemodialysis with a vascular catheter.
2. Subjects with vascular access that is determined by the clinician to be unacceptable for a hemodialysis procedure.
3. Patients with a bleeding diathesis
4. Patients receiving anti-coagulants
5. Previous vascular access surgery (≤ 30 days from study entry) or planned access surgery
6. Known hypersensitivity to any imaging agents (e.g., contrast) that may be required during the study period
7. Patients with confirmed vasculitis
8. Vascular access infection or systemic active infection within 30 days of study entry
9. Life expectancy less than 12 months
10. Planned renal transplantation or planned conversion to peritoneal dialysis
11. Subjects with any condition determined by the investigator that precludes them from safely participating in the study.
12. Female participants at the time of consent to the study cannot be breastfeeding or pregnant.

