7.3 Measures to Minimize Bias: Randomization and Blinding

The study is not randomized or blinded. Control sessions measuring the rates of adverse events and successful therapy sessions is included to provide a within-subject comparator to these rates for the V Needle. To minimize bias, subjects will be considered and asked to enroll in the study sequentially to the extent possible to ensure that no unconscious bias of patient selection occurs. The study will be conducted at multiple centers to ensure that outcomes are able to be generalized across different clinics.

At least two different clinicians will evaluate the device for each patient and for each needle for that patient (test and control) to minimize the bias associated with the same clinician evaluating all of the sessions for a given subject.

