10.1 Statistical Hypotheses

10.1.1 Sample Size

The sample size was determined to compare the rate of successful treatments between hemodialysis sessions with the test needle compared to the control needle.

The hypothesis test for the primary performance measure is defined as follows:

$$H_0: p_T - p_C \leq -\delta$$

$$H_1: p_T - p_C > -\delta$$

where p_T is the probability of a successful hemodialysis treatment session with the V Needle (test), p_C is the probability of a successful hemodialysis treatment session with a commercially available device (control), and δ is the non-inferiority margin.

This sample size estimation is based on the following assumptions:

- The expected success rate for both devices is 98%
- The expected difference between the test and control treatment groups is 0%
- There is a test-to-control sampling ratio of 2:1
- A non-inferiority margin of 8% ($\delta = 0.08$)
- Use of a one-sided Farrington-Manning Score Test with 85% power and at a one-sided 2.5% significance level

Based on these assumptions, a statistically powered sample size of 87 test (V Needle) sessions is required for the primary endpoint^{4,5}.

The total sample size is therefore determined to be 108 test sessions with 18 subjects required to account for 20% attrition and/or any of the 6 V Needle sessions being missed.

The primary performance analysis will test the non-inferiority hypothesis as a difference of proportions between the test and control groups using a one-sided Farrington-Manning Score Test at a significance level of $\alpha=0.025$.

Additionally, the primary performance measure will be analyzed on the subject-level (utilizing a non-inferiority margin of 0.05) by testing the difference in mean success rates per subject across treatment groups using a one-sided paired t-test at a significance level of $\alpha=0.025$.

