10.1.2 Primary Hypothesis

The primary performance goal for this study is that the Hemotek device will provide successful hemodialysis treatment at a rate non-inferior to that of the commercially available devices. The rate of successful treatment will be computed as the number of successful session completions of V Needle, as determined by the clinician, divided by the total number of sessions attempted.

To determine whether a dialysis session was successful, clinicians will be asked “Was dialysis session incomplete because of a vascular access issue?” If the answer is “No,” this indicates that the dialysis session completed successfully or was stopped for reasons that were not related to the vascular access (e.g., patient illness, etc.).

The null hypothesis is that the difference between the rates of successfully completed hemodialysis sessions for the test and control groups is less than or equal to the non-inferiority margin (indicating inferior success rate). Rejection of the null hypothesis indicates the observed data supports the alternative hypothesis that the difference between the rates of successfully completed hemodialysis session for the test and control groups is at least the non-inferiority margin (indicating non-inferior success rate).

The hypothesis test for the primary analysis are defined as follows:

$$H_0: p_T - p_C \leq -\delta$$

$$H_1: p_T - p_C > -\delta$$

where p_T is the probability of a successful hemodialysis treatment session with the V Needle (test), p_C is the probability of a successful hemodialysis treatment session with a commercially available device (control), and δ is the non-inferiority margin.

⁴ Chow, S.C., Shao, J., and Wang, H. 2008. Sample Size Calculations in Clinical Research, Second Edition. Chapman & Hall/CRC. Boca Raton, Florida.

⁵ Farrington, C. P. and Manning, G. 1990. 'Test Statistics and Sample Size Formulae for Comparative Binomial Trials with Null Hypothesis of Non-Zero Risk Difference or Non-Unity Relative Risk.' Statistics in Medicine, Vol. 9, pages 1447-1454.

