10.3.4 Alarm categories and definitions

The following definitions are used for dialysis machine alarms:

True Alarm: Alarm was appropriate because clinician action was required beyond resetting the alarm (e.g., venous needle dislodgement, significant needle movement, infiltration, tape failure), and/or V Needle footplate opened appropriately.

False Alarm: No clinician action was required beyond resetting the alarm, and/or V Needle footplate opened inappropriately.

The following definitions will be used for the footplate opening:

Appropriate footplate opening: Footplate opening due to a VND or infiltration and/or needle movement, tape failure, or other condition that can potentially lead to a VND or infiltration.

Inappropriate footplate opening: Footplate opening that is not due to a VND or infiltration and/or needle movement, tape failure, or other condition that can potentially lead to a VND or infiltration

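### The primary test and the 87-session size treat repeated sessions from 15 to 20 patients as independent, so the one-sided 2.5% error is not assured if failures cluster by patient

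*Combined protocol and SAP*

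**What the plan says.** Section 10.1.1 assumes 98% success with both needles, a 2:1 session ratio, a margin of 0.08, one-sided 2.5% significance and 85% power. It concludes that "a statistically powered sample size of 87 test (V Needle) sessions is required for the primary endpoint". No within-patient correlation or design effect appears among the assumptions.

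Each patient has three control sessions and then six V Needle sessions. Section 10.3.1 says "the remaining 18 subjects would contribute 108 test and 54 control sessions"; section 1.11 allows 15 to 20 subjects. On analysis it says "Data will be pooled by session type (test vs. control) from all sites (no by-site analyses are planned", and it names the one-sided Farrington-Manning test as the primary performance analysis. Section 7.3 says that measuring control sessions "is included to provide a within-subject comparator to these rates for the V Needle", so the same patients supply both groups.

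The plan also says that "the primary performance measure will be analyzed on the subject-level (utilizing a non-inferiority margin of 0.05"), using a one-sided paired t-test. Sections 10.3.1 and 10.4.1 present this as an additional analysis.

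**The concern.** The Farrington-Manning variance is that of two independent binomial samples. Here the observations are repeated sessions on a small number of patients, and the pooled statistic depends only on the totals. Two failures in one patient count the same as two failures in two patients, although the first pattern carries less independent information. If failures cluster by patient, a needle truly 8 points worse can be declared non-inferior more often than 2.5% of the time, in a study meant to support marketing clearance (section 1.5).

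The documents make clustering plausible but do not show it.

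- **For:** the failure question is "Was dialysis session incomplete because of a vascular access issue". Section 6.2 excludes patients with recent "or planned access surgery", so a patient will normally keep the same access throughout.
- **Against:** events of the kind listed in section 10.3.4, "venous needle dislodgement, significant needle movement, infiltration, tape failure", need not recur in the same patient, and each device is used once (section 7.1.1).
- **Either way:** section 3.3.3 places the added risk partly at the access site and partly in the membrane inside the needle.

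**Working it through.** **1. Reproducing 87.** Inputs from section 10.1.1: p_T = p_C = 0.98, δ = 0.08, ratio 2:1, one-sided α = 0.025. Statistic: z = (p̂_T − p̂_C + δ)/SE, where SE uses the maximum-likelihood rates constrained to p_T − p_C = −δ; reject at z ≥ 1.96. Exact enumeration, every session an independent binomial trial:

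| Test/control sessions | Power at 0.98/0.98 | Error at 0.90/0.98 |
|---|---|---|
| 86/43 | 74.4% | 2.7% |
| 87/43 | 85.3% | 2.7% |
| 87/44 | 85.5% | 2.8% |
| 90/45 | 84.6% | 2.4% |
| 108/54 | 91.3% | 2.3% |

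So 87 is the smallest test size that reaches 85%, given independent sessions.

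**2. Error under clustering.** The ICC is assumed. Simulation: six test and three control sessions per subject; each subject's success probability is drawn from a beta distribution with mean p and intraclass correlation ICC. For needle-specific effects the two needles have independent draws; for a shared effect one quantile is applied to both needles' distributions. Null: p_C = 0.98, p_T = 0.90. Ranges run from shared to needle-specific.

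| Subjects | ICC 0 | 0.05 | 0.1 | 0.2 |
|---|---|---|---|---|
| 15 | 2.4% | 2.6–3.5% | 3.1–4.9% | 4.4–7.6% |
| 18 | 2.3% | 2.6–3.5% | 3.1–4.9% | 4.4–7.5% |
| 20 | 2.3% | 2.3–3.4% | 2.5–4.5% | 3.2–6.9% |

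Power of the pooled test at 98%/98% for ICC 0 / 0.1 / 0.2 is 91% / 88–91% / 85–91% with 18 subjects and 85% / 82–85% / 80–85% with 15.

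**3. What the pooled statistic cannot see.** Take 18 subjects, control 54/54, V Needle 106/108. The constrained rates are 0.92 and 1.00.

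- SE = √(0.92 × 0.08/108) = 0.0261.
- z = (−0.0185 + 0.08)/0.0261 = 2.355, wherever the two failures fall.

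A subject-level design effect compares the between-subject variance with the binomial one:

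D = [S/(S−1) × Σ r_i²] / [p̂_T(1−p̂_T)/N_T + p̂_C(1−p̂_C)/N_C], with r_i = (y_Ti − n_Ti p̂_T)/N_T − (y_Ci − n_Ci p̂_C)/N_C.

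The denominator is 0.000168.

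- Failures in two patients: numerator 0.000161, D = 0.96, floored at 1; adjusted statistic 2.355.
- Both failures in one patient: numerator 0.000343, D = 2.04; adjusted statistic 2.355/√2.04 = 1.65, below 1.96.

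**4. The planned t-test.** At the same 8-point null with 18 subjects its error is 0.2% / 0.4–0.5% / 0.7–0.9% / 1.3–2.0% at ICC 0 / 0.05 / 0.1 / 0.2, so it is conservative there. It is undefined when no session fails. With nine sessions per subject, all independent at 98%, that has probability 0.98^135 = 6.5%, 0.98^162 = 3.8% and 0.98^180 = 2.6% for 15, 18 and 20 subjects.

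**The case against.** **The plan already has a patient-level analysis.** True, and it is conservative at the 8-point null. But it is additional, so it does not protect the conclusion drawn from the pooled test.

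**A reader might infer that nothing says which test decides.** The documents do not support that. Section 10.3.1 names the pooled test as primary, section 10.1.2 ties non-inferiority to rejection of the primary null, and section 10.1.1 sets the 0.08 margin. What is missing is an explicit supportive label for the t-test and a zero-variance rule.

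**A reader might take disagreement between the two tests as a sign of clustering.** It is mainly the margin. In the example above the 0.05-margin t statistic is 2.48 (two patients) or 1.70 (one patient) against a cut-off of 2.110. At margin 0.08 it is 4.84 or 3.32, and both pass. At 98%/98% with independent sessions, the pooled test passes and the t-test fails in 25% of trials at 18 subjects and 35% at 15. With margin 0.08 in the t-test this falls to about 2%.

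**The inflation rests on an assumed ICC.** This stands. The best argument for correlation, that the patient keeps the same access, points to a shared effect and so to the lower ends. The upper ends need needle-specific susceptibility, for which section 3.3.3 offers only a hint. At ICC 0.05 with a shared effect, the error (2.6%) is no larger than the 2.7–2.8% that discreteness alone gives at the 87-session minimum.

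**At least two clinicians assess each needle in each patient.** This limits assessor bias; it does not remove a shared access.

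**Conclusion.** The point holds in conditional form. The primary test and the stated 87 sessions with 85% power assume independent sessions, and nothing in the primary analysis allows for within-patient correlation. With 18 subjects the true error at 0.90 versus 0.98 would be about 3–5% at ICC 0.1 and 4–7.5% at ICC 0.2. It would be close to nominal if the ICC is near 0, or if it is about 0.05 with an effect shared by both needles. Power at 98%/98% is little affected.

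The stronger reading, that the error rate is shown to be inflated or that the study is too small, is not supported: the documents give no ICC and the ranges above are assumptions. Severity: should-fix.

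**What to change.** **Section 10.3.1.**

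- Keep the 8% margin and make the primary test account for the patient. One workable form is the Farrington-Manning statistic divided by √D, with D as above, floored at 1 and set to 1 if there are no failures.
- Prespecify the cut-off by simulation over a stated ICC range.
- Keep the unadjusted pooled test as a sensitivity analysis.
- Label the 0.05-margin t-test supportive and give it a zero-variance rule.

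**Section 10.1.1.** State that 87 sessions and 85% power assume independent sessions, and restate power in subjects over the ICC range, without enrolling more.

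**Cost.** Some wording, a few lines of code and lower stated power. With 18 subjects, against 91% for the unadjusted test at ICC 0:

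| Cut-off | Error, ICC 0 / 0.1 | Power, ICC 0 / 0.1 |
|---|---|---|
| 1.96 | 2.0% / 2.6–3.4% | 89% / 78–84% |
| t(17) = 2.110 | 1.2% / 1.3–2.1% | 78% / 70–78% |

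The 1.96 cut-off does not fully restore 2.5% at ICC 0.1, which is why the cut-off needs simulation. With 15 subjects, power at ICC 0 / 0.1 is 83% / 74–81% with 1.96 and 65% / 62–68% with the t cut-off.

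**Two alternatives to avoid.** Requiring both planned tests to pass would make the 5% margin binding: with independent sessions, power falls from 91% to 66% at 18 subjects and from 85% to 50% at 15. Replacing the primary test with a paired t-test at 0.08 does not secure 2.5% either; its simulated error with 18 subjects at ICC 0.1 is 3.9–5.3%.

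### The additional subject-level paired t-test can have zero variance, holds its 2.5% level only if sessions within a subject are nearly independent, and is often discordant with the 8% primary test

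*Combined protocol and SAP*

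**What the plan says.** Sections 1.21, 10.1.1 and 10.3.1 test session success twice.

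- **Primary analysis.** Sessions are pooled by needle type and compared by a Farrington-Manning score test. Section 10.1.1 plans "Use of a one-sided Farrington-Manning Score Test with 85% power and at a one-sided 2.5% significance level". The other planning inputs are "The expected success rate for both devices is 98" per cent, "The expected difference between the test and control treatment groups is 0" per cent, "There is a test-to-control sampling ratio of 2:1" and "A non-inferiority margin of 8" per cent. From these, "a statistically powered sample size of 87 test (V Needle) sessions is required for the primary endpoint".
- **Additional analysis.** The same measure is analysed per subject, "utilizing a non-inferiority margin of 0.05) by testing the difference in mean success rates per subject across treatment groups using a one-sided paired t-test", also at one-sided 0.025.

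Section 10.4.1 identifies the second analysis as additional and as the only one done within subject. The documents give no reason for a second margin, no power for the t-test, no within-subject correlation, no rule for zero variance and no statement of how to read discordant results. Section 10.4.2 (available data, no imputation) does not fill these gaps.

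**The concern.** The study uses each subject as his or her own control, and this t-test is the one planned analysis that treats the subject as the unit. Each subject contributes 6 test and 3 control sessions. At 98% success about 162 × 0.02 = 3.2 failures are expected across all 162 sessions of 18 subjects, so nearly every paired difference is zero. The t distribution is a poor reference for such data in two ways.

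- If every session succeeds, the standard deviation is zero and there is no statistic.
- If failures concentrate in a few subjects, a sample that happens to contain few of them shows a mean near zero and a very small standard deviation, so the test rejects too easily.

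The stricter margin also gives the test much less power than the primary analysis. A sponsor with a device exactly as good as assumed could have to explain a failed non-inferiority test, with no prior rule for doing so, in a study meant to support marketing clearance.

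**Working it through.** **Inputs.** 98% success on both needles, primary margin 0.08, one-sided 2.5% (Section 10.1.1); 3 control and 6 test sessions per subject, subject-level margin 0.05 (Section 10.3.1); 15 to 20 subjects (Section 1.11). Within-subject correlation is not in the documents and is varied as an assumption.

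**1. The plan's own figure.** Exact binomial enumeration of the Farrington-Manning test at 98%/98% gives power of 74.4% at 86/43 test/control sessions, 85.3% at 87/43 and 85.5% at 87/44. The stated 87 reproduces. The plan gives no power for the t-test, so there is none to reproduce.

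**2. The statistic.** For subject i, D = x_T/6 − x_C/3, and t = (mean D + 0.05) / (SD/√n). It is compared with the 97.5% point of t on n − 1 degrees of freedom (2.110 at n = 18).

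**3. Zero variance.** If all 9n sessions succeed, every D is 0 and t = 0.05/0. With independent sessions the probability is 0.98^(9n):

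- 15 subjects: 0.98^135 = 6.5%
- 18 subjects: 0.98^162 = 3.8%
- 20 subjects: 0.98^180 = 2.6%

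Simulation gives 6.6%, 3.7% and 2.7%. At latent correlations of 0.3 to 0.5 the share rises to about 6-18%.

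**4. One discordant data set.** Take 18 subjects with three test failures in three different subjects and no control failure.

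- t-test: mean D = −3 × (1/6)/18 = −0.0278; SD = (1/6)√[(3/18)(15/18)(18/17)] = 0.0639; SE = 0.0639/√18 = 0.0151; t = 0.0222/0.0151 = 1.48, below 2.110, so it fails.
- Primary: 105/108 versus 54/54. The restricted estimates are 0.92 and 1.00, so SE = √(0.92 × 0.08/108) = 0.0261 and z = (−0.0278 + 0.08)/0.0261 = 2.00, above 1.96, so it passes.

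**5. Simulation at 98%/98%, independent sessions** (40,000 or more trials per setting):

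| Subjects | Primary power | t-test power, undefined = pass | t-test power, undefined = fail | Primary passes, t-test fails (undefined = pass) |
|---|---|---|---|---|
| 15 | 84% | 50% | 43% | 34% |
| 18 | 91% | 66% | 62% | 25-26% |
| 20 | 90% | 62% | 59% | 28% |

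The reverse pattern does not occur here. With a shared latent-normal subject effect at correlation 0.3 to 0.5, primary-pass/t-fail discordance is about 18-27%.

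**6. Size at the 5-point null (93% test, 98% control), nominal 2.5%:**

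| Assumed latent correlation | Size, 15-20 subjects |
|---|---|
| 0 | 2.0-2.7% |
| 0.1 | about 3-4% |
| 0.3 | about 5-7% |
| 0.5 | about 8-10% |

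Other clustering models agree in direction. A shared beta-binomial effect with intraclass correlation 0.05 to 0.30 gives 3.4-9.5% at 15 subjects and 4.3-11.9% at 18. A logit-normal intercept with SD 1 to 2 gives 3.6-10.3%. Skewness alone can do it: at 94% versus 99% with 18 independent subjects the size is 4.6%.

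**7. Would a common 0.08 margin cure this?** At 98%/98% with independent sessions, total disagreement falls to 8.1%, 4.7% and 7.1% at 15, 18 and 20 subjects. Most of it is now the reverse pattern, primary fails and t-test passes (6.0%, 3.1% and 6.5%). Size at 90% versus 98% is still 5.6-6.4% at correlation 0.3 and 8.4-9.5% at 0.5.

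**The case against.** The t-test is an additional analysis. Sample size and power are tied only to the primary test, and nothing makes the t-test a success criterion. A stricter margin in a supporting analysis is a legitimate choice, and low power in an unpowered analysis is not an error. The undefined case arises essentially when every session succeeds; the primary test then passes, so no decision is in doubt. The inflated size depends on a correlation the documents do not give. It is near nominal with independent sessions, and at 88% versus 93% it stays at 1.7-2.2% for correlations of 0.05 to 0.2.

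Most of this stands, and it limits the point. A reader might infer that the two tests contradict each other. They do not: passing at 8 points and failing at 5 means that a loss of 8 points or more is excluded while a loss of 5 is not. A reader might also infer that the t-test has no usable error rate under any conditions, or that the primary conclusion is unsafe because of it. The independent-session figures do not support the first, and the separate role given to the primary analysis does not support the second.

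What the objection does not answer is that the plan attaches a margin and a 0.025 level to this test, so it reads as pass/fail. Under correlated sessions, which a subject-level analysis exists to handle, that level is not assured. In the best possible outcome the specified statistic cannot be computed.

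**Conclusion.** The subject-level test is wrong as written: neither a computable statistic nor the stated 2.5% level is assured on these data. The zero-variance and discordance figures (about 3-7% and 25-34% of trials) rest on the plan's own 98%/98%, with sessions taken as independent. Discordance counts undefined trials as t-test passes; counting them as failures makes it 29-41%. The excess size is conditional on assumed clustering and should be reported as a range, from nominal at zero correlation to roughly four times nominal at 0.5. The consequence is a supporting result that is hard to interpret. It should be settled before the data are analysed, but it does not invalidate the primary analysis.

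**What to change.** In Sections 1.21, 10.1.1 and 10.3.1:

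1. State that the subject-level analysis is supportive and descriptive: report the mean paired difference with an interval and make no pass/fail claim at 0.025. State that discordance does not alter the primary conclusion.
2. Specify that when all paired differences are zero the t-test is not computed, and the observed zero difference is reported alongside the primary result.
3. Justify the 0.05 margin, or say that it is a deliberately stricter sensitivity margin. Moving it to 0.08 is optional: it leaves about 5-8% total disagreement and does not repair the size.
4. If a p-value is kept, obtain it by simulation at the null boundary over a pre-specified range of within-subject correlations and report the largest. Do not take it from the t distribution, or from a correlation estimated from about three failures.

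The cost is wording in three sections, a short simulation program if item 4 is used, and the loss of a formal subject-level pass/fail claim.
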